Aim 1 (Focus Groups): We will conduct six FGs, four with HIV+ cocaine users and two with healthcare providers, comprised of 6-8 persons each. For the PLH FGs, we will recruit PLH who primarily use cocaine, from clinical care and community outreach programs in New Haven, CT. Of the four PLH FGs, one will consist solely of men and one solely of women in order to address possible gender differences. Eligibility criteria will be: a) ≥ 18 years; (b) speaks English or Spanish; c) HIV+; d) self-reported cocaine use in the previous 30 days; and e) able to give informed consent. For the two healthcare provider FGs, we will recruit physicians, nurses, clinic supervisors, and substance abuse counselors from HIV clinics. We will target representation from the 5 HIV clinics in New Haven.

Aim 2 (Pilot Feasibility Study): We will recruit 90 participants from HIV care clinics and drug treatment programs in New Haven. Eligibility criteria will include: 1) clinic-confirmed HIV diagnosis; 2) ≥ 18 years; 3) prescribed or eligible (clinician willing to prescribe) for ART; 4) currently have insurance coverage; 5) self-reported cocaine use in the past 6 months; and 6) and willing and able to use an electronic pill box and blister pack for study duration. This will be a 16-week study with a 12-week intervention and 4-week post-intervention observation period.

Sample Size and Power Calculations: The literature suggests that effect size calculations may not be appropriate for pilot RCTs.¹¹⁵ Thus, based on a review of pilot studies that have ranged in sample size from 12 per group¹¹⁶⁻¹¹⁸ to 9%-50%^{119,120} of the proposed larger RCT's sample size (generally 30 per arm); we propose to enroll 20 participants for groups A, B, and C. For Group D, we propose to enroll 30 participants so that hypotheses #7 (There is statistically significant difference between a patient's ART adherence and persistence and HIV outcomes when their designated social network member lives inside vs outside patient's activity space) can be tested. Therefore, a total of 90 study participants for the pilot feasibility RCT is proposed. This sample size is appropriate in order to refine study procedures, develop a final intervention manual and prepare for a future large-scale RCT.

NOTE: Is this research proposal designed to enroll children who are wards of the state as potential subjects? Yes No (If yes, see Instructions section VII #4 for further requirements)

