- b. Plan for subjects who develop serious psychiatric/medical symptoms during the follow-up phase: If the subjects develop serious DSM-V psychiatric symptoms or medical symptoms they will have many opportunities to report their symptoms with not only the clinicians but also the RA who will be available 7 days a week by telephone. If serious symptoms are reported, the participants will be evaluated by the PI of the study, [name] who is board-certified in Internal Medicine, Infectious Diseases and Internal Medicine. If [name] determines that the subjects' medical or psychiatric symptoms cannot be treated as outpatients, they will be admitted to the local hospital Emergency Room. Furthermore, the subjects' chronic medical primary care providers will be notified immediately of any changes in their psychiatric or medical condition to continue with follow-up.
- c. Notification to HIV physicians due to lack of ART adherence or persistence: During the RCT, if participants are found to be non-adherent or non-persistent to their ART medication, where a risk of HIV virus can mutate to become resistant to the current regimen, their physician will be notified.¹³⁵ When an individual is enrolled in the study, he/she will be asked to provide us with the name of their physician and sign a medical release of information (ROI) allowing us permission to communicate with the physician as need. A letter will be faxed to the physician's office stating that the participant is enrolled in an ART adherence study; this initial communication will also request notification of any medication changes. Additional communication with the provider will include phlebotomy results and information if the participant is found to be non-compliant to their ART regimen (missed 2 weeks or more of medications).
- d. Halting Rules for the Study: A DSMP, similar to a DSMB, may institute a number of pre-planned rules for halting the study or modifying the study design. For pilot studies of this size, when there is not expected to be a difference in efficacy anticipated, there will be no halting rules aside from adverse events. For the purposes of this study, a pre-planned interim analysis is planned when 50% of the subjects are accrued and have completed 6 weeks of the study. This time point is based upon efficacy outcomes when the primary measure of interest can be assessed.

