Aim 2 (Pilot Feasibility Study): The primary outcomes will be ART adherence and persistence, measured as a composite score ranging from 0 to 100%, and as number of continuous days taking ART without a 7-day (or 3-day) gap^{18,71} respectively. Outcome analyses will be conducted for (a) adherence and persistence behavior, (b) drug outcomes (cocaine use), (c) HIV treatment outcomes (VL<20 copies/mL; change in CD4+ T lymphocytes), and (d) ART-related Information, Motivation, and Behavioral Skills constructs. The general framework for discerning differences between study conditions on main outcome variables will be to perform 3 (intervention condition) x 3 (repeated follow-up assessments) mixed design analysis entering pre-intervention scores as covariates and additional theoretically and empirically relevant covariates (such as baseline mental status etc.). For variables that are approximately normally distributed, we will use multivariate analyses of covariance (MANCOVA), with significant multivariate tests followed by subsequent analyses of co-variance (ANCOVA). Variables that violate distributional assumptions of normality will be analyzed using generalized linear model (GLM) procedures, which enable the use of non-Gaussian error models. Based on a review of the literature, GLM is the most appropriate approach for variables with strong positive skew, e.g., adherence.

[figure not shown]
To examine the mediating and moderating effects of activity space and social network facilitators and barriers on primary (ART adherence and persistence) and secondary outcomes (HIV viral suppression, cocaine use, retention in HIV care), the following steps are going to be followed:

- a. A range of variables associated to activity space and social networks (both risk and support) will be calculated using a combination of GIS, SNA, and spatial statistics methods. The variables will be the covariates.
- b. The outcome variables are: primary (ART adherence and persistence) and secondary outcomes (HIV viral suppression, cocaine use, retention in HIV care).
- c. We will first use descriptive statistics, bivariate correlation, and t-tests to understand the distribution and association of all the covariates calculated in step#a with the outcome variables (step#b).
- d. After running tests of multicollinearity, only uncorrelated covariates at $p \leq 0.05$ (considered statistically significant) will be included in the subsequent mediation and moderation analysis.

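### For outcomes treated as approximately normal, the outcome-level ANCOVA depends on a significant MANCOVA, and the plan commits to no arm difference with an interval when that test is not significant

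*Combined protocol and SAP*

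**What the plan says.** Section 12, Aim 2, sets a general framework: "perform 3 (intervention condition) x 3 (repeated follow-up assessments) mixed design analysis entering pre-intervention scores as covariates". It then splits the outcomes by distribution.

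- Approximately normal variables: "we will use multivariate analyses of covariance (MANCOVA), with significant multivariate tests followed by subsequent analyses of co-variance (ANCOVA".
- Other variables: "Variables that violate distributional assumptions of normality will be analyzed using generalized linear model (GLM) procedures". No multivariate step is attached to this route. Adherence is the named example: "GLM is the most appropriate approach for variables with strong positive skew, e.g., adherence".

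The outcome list has adherence and persistence, cocaine use, and then "c) HIV treatment outcomes (VL<20 copies/mL; change in CD4+ T lymphocytes), and (d) ART-related Information, Motivation, and Behavioral Skills constructs". Apart from adherence, no outcome is assigned to a route.

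On size, Sample Size and Power Calculations says "we propose to enroll 20 participants for groups A, B, and C", with 30 for group D. It declines effect-size calculations and gives this purpose: "This sample size is appropriate in order to refine study procedures, develop a final intervention manual and prepare for a future large-scale RCT". The halting rules in section 11 (item d) describe pilots of this size as a setting "when there is not expected to be a difference in efficacy anticipated".

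**The concern.** A pilot is most useful to its successor when it hands over estimates, intervals and SDs regardless of statistical significance. On the normal-outcome route, the outcome-level analysis is run only after a joint test succeeds. With about 20 per arm, and no efficacy difference anticipated by the plan itself, that test will often fail if effects are small. When it succeeds, it does so in samples where the observed differences happen to be large, so the estimates that follow are biased away from zero.

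This is separate from missing data and multiplicity; it arises with complete data and one family of outcomes. At stake are the figures for CD4 change (part of hypotheses 2 and 5), the IMB constructs, and possibly persistence and cocaine use.

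**Working it through.** **The plan's own figure.** 3 x 20 + 30 = 90, which matches the stated total. The documents give no power, effect size or alpha for the arm comparisons, so there is no power figure to reproduce.

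**Which outcomes are gated.**

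| Outcome | Route under section 12 | Gated? |
|---|---|---|
| Adherence (0-100%) | GLM, named | No |
| VL<20 copies/mL | Binary, so not a MANCOVA variable | No |
| CD4 change, IMB scores | Not assigned; plausibly normal | Likely |
| Persistence (days), cocaine use | Not assigned; may be skewed | Possible |

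**Gate.** Wilks' lambda = |E| / |E + H|, with Rao's F approximation on df1 = p x q, where p is the number of outcomes and q = arms - 1. With four arms and p = 4, df1 = 4 x 3 = 12. The gate opens if P < 0.05. The ANCOVA estimate of C-A is then recorded over all simulated trials and over those where the gate opened.

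**Assumptions not in the documents.** The 0.05 level; 2 to 4 gated outcomes; correlations of 0.3 to 0.6; the true difference d in SD units; complete data; one time point, so the repeated-assessment factor is ignored. There were 4,000 simulated trials per setting in the first two sets.

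**Results, arms 20/20/20/30.**

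Set 1: B at d/2, C and D at d above A; 2 or 4 outcomes correlated 0.3 or 0.6; baseline covariates unrelated to outcome.

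| d | Gate opens | Mean C-A if open / truth |
|---|---|---|
| 0.2 | 7-9% | 1.8-2.1 |
| 0.3 | 11-14% | 1.5-1.8 |
| 0.5 | 24-35% | 1.3-1.4 |
| 0.8 | 59-81% | 1.06-1.15 |

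Set 2: A = B, C and D at d above them; 3 outcomes correlated 0.5; baseline correlated 0.5 with outcome.

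| d | Gate opens | Mean C-A if open / truth | 95% CI coverage if open |
|---|---|---|---|
| 0.2 | 11% | 0.334/0.2 = 1.67 | 86% |
| 0.3 | 21% | 0.434/0.3 = 1.45 | 87% |
| 0.5 | 57% | 0.591/0.5 = 1.18 | 94% |

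A further set of simulations gave, at 0.2-0.3 SD, about 7-27% opening, ratios of about 1.5-2.1 and coverage of 76-90%. At 0.5 SD it gave 32-67% opening, ratios of 1.1-1.3 and coverage of 92-95%.

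**Checks.** With d = 0 the gate opens in about 5% of trials with no systematic shift. Without the gate, the mean C-A estimate is 0.20-0.21 for d = 0.2, 0.29-0.30 for 0.3, 0.49-0.51 for 0.5 and 0.79-0.81 for 0.8, so the bias comes from the gate. If the three-condition wording is taken literally (20/20/20), the figures are worse: at d = 0.3, 10-12% open with ratios of 1.75-2.1.

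**Consequence if the estimates were used for sizing.** Required n varies as 1/d^2. An effect overstated 1.5-fold gives 1/1.5^2 = 1/2.25, or 44% of the needed sample; overstated 2.1-fold, 1/2.1^2 = 1/4.41, or 23%. At 0.5 SD, 1.1-fold to 1.4-fold gives 1/1.21 to 1/1.96, or 83% to 51%.

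**The case against.** MANCOVA followed by ANCOVA is a conventional sequence that gives some protection against false positives. The section orders tests; it never says that estimates are withheld. With the same design matrix, the MANCOVA's own coefficients equal the ANCOVA coefficients, and its error matrix supplies the residual SDs. A statistician could report these after a null multivariate test without breaking the plan. That stands: the defect is a conditional analysis step with no commitment to report, and not a ban on reporting.

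Three stronger readings are tempting, and the documents do not support them.

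- A reader might infer that most outcomes would go without an estimate and the rest would be inflated. The gate covers only approximately normal variables, and one joint test opens or closes it for the whole block.
- A reader might infer that hypotheses 1 to 6 go unanswered after a null MANCOVA. Hypotheses 1 and 4 include adherence, which goes to an ungated GLM. Retention in care (hypotheses 2 and 5) is stated as a rate, so it is not evidently a MANCOVA variable.
- A reader might infer that the next trial will be undersized. The plan says the pilot prepares a large RCT; it does not say that the RCT will be sized from these differences.

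The numbers also rest on assumed effects and correlations, and the distortion fades as the true effect grows.

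**Conclusion.** The point holds for the approximately normal outcomes only. If true differences are 0.2-0.3 SD, the ANCOVA step would be skipped in roughly 73-93% of trials (100 minus 27, 100 minus 7). The estimates that pass would be about 1.5-2.1 times too large, with intervals that cover too rarely. At 0.5 SD the overstatement is about 1.1-1.4 times and coverage is near nominal, somewhat lower where the gate opens least often. At 0.8 SD little is left of the problem. These are conditional figures under stated assumptions, not predictions for this trial.

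The plan expects no efficacy difference at this size, so small effects are the case to guard against. Any later use of the gated estimates for planning would then rest on figures that are absent or too large. The change should be made, but it does not affect the analysis of adherence or of VL<20.

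**What to change.** In section 12, Aim 2, replace the conditional sequence with:

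> For each approximately normal outcome, the covariate-adjusted differences C-A, C-B, D-A and D-B with 95% CIs, and the residual SD, will be reported whether or not the multivariate test is significant. For GLM outcomes, the same contrasts will be reported on the model's scale with 95% CIs. Any multivariate test is descriptive and does not decide which outcomes are estimated.

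The residual SD is asked for only on the normal route, because it has no useful meaning for a binary outcome such as VL<20. The section should also state which route persistence, cocaine use, CD4 change and the IMB scores take, and replace the three-condition framework with one that covers all four arms.

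The cost is analysis-plan wording and a longer results table; data collection and conduct do not change. The omnibus test's partial error protection is lost, so the differences should be presented as estimates with intervals and not as confirmatory tests.

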After the 12-week intervention, all participants will be followed for a 4-week period and primary and secondary outcomes will also be recorded during the post-intervention follow-up period.

3. Monthly Research Interviews: Monthly interviews will take place for the 16-week duration of the study (12-week intervention and 4-week follow-up) for all participants. The interviews will include health care utilization, phlebotomy, self-reports of drug use, and mental illness. All phlebotomy information obtained after community release will be obtained through Quest Diagnostics, a national reference laboratory. We have a prearranged system for phlebotomy, reporting of results and storing specimens at -70C that has been in place for the past decade. None of the assays used are experimental and will be drawn as part of clinical care at standardized times as outlined. Tests will include HIV-1 RNA testing (Amplicor 1.5, range 50 to 750,000 copies/mL) and CD4 lymphocyte count using flow cytometry at baseline, end of intervention (12 weeks) and end of follow-up period (16 weeks). HIV genotypic mutations will be assessed at baseline and at 16 weeks (if VL>500 copies/mL).

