- e. Using the framework of structural equation modeling, we will identify the moderating and/or mediating effects of spatial (activity space and neighborhood levels) and non-spatial data (individual and interpersonal) covariates on the primary and secondary outcomes.

A comparative analysis will be conducted to contrast the model performance (R², AIC, and RMSE) of two mediation/moderation models with the primary (ART adherence) and a secondary (HIV viral suppression) outcome: 1) with social network metrics and b) with spatial-social network metrics (calculated in step#a).

SECTION VII: RECRUITMENT/CONSENT AND ASSENT PROCEDURES

1. Targeted Enrollment: Give the number of subjects:

a. targeted for enrollment at Yale for this protocol ____

Aim 1 (Focus Groups): 42 (30 PLH cocaine users; 12 healthcare providers)

Aim 2 (Pilot Feasibility Study): 90 PLH with co-occurring CUD

b. If this is a multi-site study, give the total number of subjects targeted across all sites ____

2. Indicate recruitment methods below. Attach copies of any recruitment materials that will be used.

- | | | |
|--|---|-------------------------------------|
|  Flyers |  Internet/Web Postings |  Radio |
|  Posters |  Mass E-mail Solicitation |  Telephone |
|  Letter |  Departmental/Center Website |  Television |
|  Medical Record Review |  Departmental/Center Research Boards |  Newspaper |
|  Departmental/Center Newsletters |  Web-Based Clinical Trial Registries | |
|  YCCI Recruitment database |  Clinicaltrials.gov Registry (do not send materials to HIC) | |
|  Other (describe): | | |

Upon funding of this study, flyers will be created.

3. Recruitment Procedures:

- a. Describe how potential subjects will be identified.
- b. Describe how potential subjects are contacted.
- c. Who is recruiting potential subjects?

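### The activity-space and social-network models do not name the baseline value of the outcome, so baseline status can appear as a network effect on main-effect and mediator-to-outcome paths and in the model comparison.

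*Combined protocol and SAP*

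**What the plan says.** All references are to 12. Statistical Considerations, Aim 2, unless stated.

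- **Between-arm analysis.** Differences between study conditions are tested in a "mixed design analysis entering pre-intervention scores as covariates", with further covariates such as baseline mental status.
- **Network analysis.** This is a separate sequence, steps a-e. Step a builds the predictors: "A range of variables associated to activity space and social networks (both risk and support) will be calculated using a combination of GIS, SNA, and" (the sentence continues). It then states "The variables will be the covariates". Step b lists the outcomes: adherence, persistence, viral suppression, cocaine use and retention in care. Step c relates the step-a variables to those outcomes by descriptive statistics, bivariate correlations and t-tests. Step d tests multicollinearity and applies a p ≤ 0.05 rule for uncorrelated covariates; what passes "will be included in the subsequent mediation and moderation analysis". Step e fits structural equation models with "spatial (activity space and neighborhood levels) and non-spatial data (individual and interpersonal) covariates". The individual-level covariates are not listed.
- **Model comparison.** "A comparative analysis will be conducted to contrast the model performance (R², AIC, and RMSE) of two mediation/moderation models", one with social network metrics and one with spatial-social network metrics, for adherence and viral suppression.
- **Baseline data.** Under 2.E Study Procedures (Monthly Research Interviews), the tests are HIV-1 RNA and "CD4 lymphocyte count using flow cytometry at baseline, end of intervention (12 weeks) and end of follow-up period (16 weeks"). Risks Associated with Standardized Assessments lists one battery for baseline and monthly interviews. It includes the Timeline Follow-Back (TLFB) and ASI-Lite for cocaine use, and a visual analog scale (VAS) and a brief scale for adherence. Blister-pack photographs run only over the 12-week intervention and 4-week follow-up.

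**The concern.** In the between-arm analysis, randomisation already protects against bias and baseline adjustment mainly adds precision. Network and activity-space variables are not randomised. A participant's support and risk networks may well be related to adherence, suppression and cocaine use before enrolment, and those states tend to persist. A model of follow-up status without the baseline value can then credit the network metric with an association that only carries baseline forward. The section names the adjustment where confounding is least likely and is silent where it is most likely.

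Step d adds a second risk. If the baseline value were offered as a candidate covariate, a rule that keeps only uncorrelated covariates could remove it precisely when it is correlated with a network metric, which is the case in which it is needed.

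At stake are the main-effect and mediator-to-outcome paths in step e, and the comparison by R², AIC and RMSE, which could favour whichever metric set is the better proxy for baseline status. Sample Size and Power Calculations says the pilot is to prepare a large-scale trial, so a spurious network effect could misdirect that design.

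**Working it through.** **Inputs from the documents.** Arms of 20, 20, 20 and 30 (Sample Size and Power Calculations): 3 × 20 + 30 = 90, which reproduces the stated total. The plan gives no effect size, SD, correlation or power, so there is no power figure to reproduce.

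**Assumptions, not in the documents.** g = correlation of a network metric with the baseline outcome, 0 to 0.3. ρ = correlation of baseline with follow-up, 0.3 to 0.7. b = standardised network effect, 0.25 for power. Two-sided 5%, no dropout.

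**1. Spurious significance, continuous outcome.** With no association given baseline, the marginal correlation is r = g × ρ. By Fisher's z, the chance of significance is Φ(z − 1.96) + Φ(−z − 1.96), with z = atanh(r) × √(90 − 3). Example: g = 0.3 and ρ = 0.5 give r = 0.15, z = 1.41, chance 29.1%.

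| g | ρ = 0.3 | ρ = 0.5 | ρ = 0.7 |
|---|---|---|---|
| 0 | 5.0% | 5.0% | 5.0% |
| 0.2 | 8.7% | 15.5% | 26.0% |
| 0.3 | 13.4% | 29.1% | 51.1% |

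Linear-model simulation (6,000 runs per cell) agrees: 13.6%, 29.7% and 52.0% in the last row. With the baseline value in the model, the simulated rate for g = 0.2 and 0.3 is 4.7% to 5.3%.

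**2. Spurious significance, binary outcome and binary baseline** (3,000 runs per cell, linear probability model). Over g = 0.2 to 0.3 and ρ = 0.3 to 0.7, the rate is 7.5% to 31.6% unadjusted and 5.2% to 7.9% adjusted.

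**3. Power, b = 0.25, g = 0.** Adjustment multiplies residual variance by 1 − ρ², so the partial correlation is 0.25 / √(1 − ρ²), tested with one fewer degree of freedom.

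| ρ | Residual variance factor | Continuous, without → with baseline | Binary (simulated), without → with baseline |
|---|---|---|---|
| 0.3 | 0.91 | 66.4% → 70.1% | 42.5% → 43.9% |
| 0.5 | 0.75 | 66.4% → 78.7% | 44.2% → 47.5% |
| 0.7 | 0.51 | 66.4% → 92.4% | 45.7% → 53.8% |

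The gains are about 4, 12 and 26 points for a continuous outcome and about 1, 3 and 8 for a binary one.

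**4. Moderation by randomised arm** (30 against 60, g = 0.3, no arm-by-baseline effect, 4,000 runs). The arm-by-metric term is significant 4.8% of the time at ρ = 0.5 and 4.9% at ρ = 0.7 without baseline. There is no inflation.

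**5. Proxy baseline for adherence.** Suppose self-report carries only a share of the variance of true baseline adherence. With g = 0.3, the partial correlation given the proxy leaves a spurious rate of 7%, 12% and 21% (ρ = 0.3, 0.5, 0.7) at a share of 50%, and 6%, 8% and 12% at a share of 70%. The unadjusted rates are 13%, 29% and 51%.

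**The case against.** **Step e does not confine the models to network and spatial variables.** A reader might infer from step a that baseline status is excluded. The documents do not support that: step e admits individual-level covariates and leaves them undefined. The fair statement is that the baseline outcome is unspecified. This does not settle the matter, because nothing forces it in and step d could drop it.

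**Moderation.** A reader might infer that moderation findings are biased too. For moderation by randomised arm the calculation shows no inflation, unless baseline itself modifies the arm effect.

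**Power.** Viral suppression is defined by VL < 20 copies/mL, so it is binary, and the plan describes adherence as strongly skewed. The larger power gains therefore do not carry over to suppression. The bias argument carries the point, not power.

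**Availability.** It would be wrong to say that every outcome has its own baseline. Adherence before the intervention is self-report only, no baseline measure of persistence is described, and participants eligible for but not yet on ART have no baseline adherence to report. Working step 5 shows that a proxy removes only part of the confounding. This limits the remedy for adherence but not for viral load or cocaine use.

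**Estimand.** Networks may already have shaped baseline status. Conditioning on baseline removes that pathway and answers a narrower question. This stands and must be stated. Step c is worded as descriptive, so its unadjusted associations can remain for the broader question.

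**Scale.** This is a secondary analysis in a pilot, and every magnitude rests on assumed correlations. Both are true. The data needed are largely in hand and the change is small.

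**Conclusion.** The concern holds in a limited form. Steps a-e and the model comparison do not name the baseline outcome, while the between-arm analysis does ("entering pre-intervention scores as covariates"). For non-randomised network metrics this leaves main-effect paths, mediator-to-outcome paths and the R²/AIC/RMSE comparison open to confounding by baseline status.

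At n = 90, with g of 0.2 to 0.3 and ρ of 0.3 to 0.7, the spurious-significance rate for a continuous outcome is about 9% to 51% unadjusted and about 5% when the same measure is adjusted for. It is 5% either way if the metric is unrelated to baseline. The power gain is about 4 to 26 points for a continuous outcome and 1 to 8 for a binary one. These ranges rest on assumed correlations and full follow-up. The change should be made, but the point does not touch the between-arm analysis.

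**What to change.** In step e and in both models of the comparative analysis, force in the baseline value of the same outcome and study arm, exempt from the step-d screen:

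- viral suppression: baseline log10 HIV-1 RNA;
- cocaine use: baseline TLFB;
- adherence and persistence: baseline VAS plus an indicator for being on ART at baseline, noting that self-report is a proxy and removes only part of the confounding.

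List the individual-level covariates meant in step e. Keep the bivariate associations of step c, labelled descriptive only. State that the models estimate the association given baseline.

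**Cost.** Wording only, with no new data collection. The baseline terms use one or two degrees of freedom per model. Four arms add 4 − 1 = 3 more where arm is not already in the model. Any network effect already expressed in baseline status is no longer counted, which is why the estimand must be stated.

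### Step d screens mediation/moderation covariates by a p ≤ 0.05 test rather than by the size of collinearity, and may remove much of the spatial-social set

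*Combined protocol and SAP*

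**What the plan says.** The steps are in the combined protocol and SAP, Section 12 (Statistical Considerations), Aim 2.

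- Step a: "A range of variables associated to activity space and social networks (both risk and support) will be calculated". The variables are neither listed nor counted.
- Step c uses descriptive statistics, "bivariate correlation, and t-tests to understand the distribution and association of all the covariates calculated in step#a with the outcome variables".
- Step d: "After running tests of multicollinearity, only uncorrelated covariates at" p ≤ 0.05, with the continuation "considered statistically significant) will be included in the subsequent mediation and moderation analysis". No collinearity test is named, and there is no VIF, tolerance or |r| threshold. Nothing says which member of a correlated pair is removed, and no adjustment for multiple pairs is stated.
- Step e: "Using the framework of structural equation modeling, we will identify the moderating and/or mediating effects of spatial" and non-spatial covariates.
- After step e, two mediation/moderation models are contrasted on R², AIC and RMSE: "1) with social network metrics and b) with spatial-social network metrics (calculated in step#a".

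The sample size comes from Sample Size and Power Calculations, under Subject Population: "Therefore, a total of 90 study participants for the pilot feasibility RCT is proposed".

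**The concern.** Collinearity harms a model through its size, which inflates standard errors and makes coefficients unstable. A p-value for a correlation also depends on n: as n grows, ever smaller correlations become significant, so a larger study would discard more covariates for no gain in stability. With many pairs tested at an unadjusted 0.05, some covariates would be discarded by chance alone.

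The setting makes this more than a technicality. The step-a variables describe the same participants' networks and activity spaces, so moderate correlation among them is plausible, though the documents give no figures. Structural equation modelling accommodates correlated covariates. If a network metric is to be modelled as carrying the effect of a spatial metric, the two must be correlated, and the filter would then remove the relation under study. What is at stake is whether the contrast of social with spatial-social metrics reflects the metrics themselves or whichever of them survive an arbitrary screen.

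**Working it through.** **Inputs.** From the documents: 20 participants in each of groups A, B and C and 30 in group D, and the threshold p ≤ 0.05. Assumed, because the documents are silent: a two-sided test; 5, 10 or 20 candidate covariates; and a common true pairwise correlation ρ between 0 and 0.5.

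**Sample size.** 3 × 20 + 30 = 90, which matches the plan's total.

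**Smallest correlation that the rule excludes.** r = t / √(n − 2 + t²), with t the 0.975 quantile on n − 2 degrees of freedom. For n = 90, t = 1.987, so r = 1.987 / √(88 + 3.949) = 0.207. The pairwise VIF is 1 / (1 − r²) = 1 / (1 − 0.043) = 1.045, and standard errors are inflated by √1.045 = 1.022, or 2.2%. With an assumed 20% loss (n = 72), the critical |r| is 0.232 and the VIF 1.057. For scale, a VIF of 5 corresponds to a pairwise |r| of √(1 − 1/5) = 0.894.

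**Chance that a pair is flagged at n = 90 (Fisher z).** For true r = 0.3: atanh(0.3) × √87 = 0.3095 × 9.327 = 2.887, and Φ(2.887 − 1.96) = 0.82. The same calculation gives about 15% at r = 0.1, 47% at 0.2 and 99.9% at 0.5.

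**False flags when all covariates are independent.** The chance of at least one is 1 − 0.95^m for m pairs, treating pairs as independent. Five covariates (10 pairs) give 40%, ten (45 pairs) 90%, and twenty (190 pairs) about 100%.

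**Covariates retained.** Simulation with 2,000 runs per case, equicorrelated normal covariates and n = 90. The plan does not say how a flagged pair is resolved, so two versions were run. For 10 candidates:

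| True ρ | Mean kept, one of each flagged pair | Mean kept, every flagged covariate dropped | Mean maximum VIF of the full set |
|---|---|---|---|
| 0 | 8.2 | 6.3 | 1.21 |
| 0.1 | 6.3 | 2.7 | 1.30 |
| 0.2 | 3.6 | 0.3 | 1.50 |
| 0.3 | 1.9 | 0.01 | 1.74 |
| 0.5 | 1.0 | 0 | 2.50 |

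With one of each pair kept, 5 candidates fall from 4.6 kept at ρ = 0 to 1.5 at ρ = 0.3, and 20 candidates from 13.9 to 2.4. For 10 candidates at ρ = 0.3 the 95th percentile of the maximum VIF is 2.05, so a VIF-above-5 rule would almost never drop anything in the case where the significance rule leaves about 2 of 10.

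**The case against.** The strongest objection is that step d can be read another way. The tests of multicollinearity may be a separate procedure such as VIF, and p ≤ 0.05 may refer back to the step-c associations with outcomes. The parenthesis about statistical significance describes the covariates that are included, which fits that reading better than a rule retaining non-significant pairs. If so, the critical correlation and VIF above do not describe the rule. This reading is possible, but less natural, because the threshold directly qualifies the word uncorrelated. Nor does it rescue the step: covariates would be picked by univariate outcome p-values, and the collinearity check would have no threshold at all.

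Second, a reader might infer that the filter certainly destroys the spatial-social comparison. The documents do not support that. With true correlations of 0 to 0.1 and one of each pair kept, most covariates survive. The comparison also refers to metrics "with spatial-social network metrics (calculated in step#a", which could mean the full unscreened set. Against this, the models compared are mediation/moderation models, and step d governs what enters those. The text leaves the matter open.

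Third, a reader might infer that the estimated effects are biased. Bias would arise if a dropped covariate were a confounder or mediator, but the documents identify none, so this is a risk and not a finding. Nor do they restrict steps a to e to group D, so critical values at n = 30 have no stated application.

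Finally, this is exploratory work in a pilot, and the arm comparison uses a separate mixed-design framework. That stands, and it limits the weight of the point.

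**Conclusion.** The point holds on the natural reading of step d. The rule uses an unadjusted significance test where a measure of magnitude is needed, and at n = 90 it can exclude covariates at |r| of about 0.21 (pairwise VIF about 1.05). It is also incomplete, since it does not say which of a pair is dropped.

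The size of the loss depends on assumptions that the documents cannot settle. With 10 equicorrelated covariates and one of each flagged pair kept, it runs from about 2 of 10 lost at ρ = 0 to about 8 of 10 lost at ρ = 0.3; if every flagged covariate is dropped, almost none remain at ρ = 0.3. The supportable conclusion is that the rule may remove much of the spatial-social set, not that it will. The change is worth making because step d cannot be carried out reproducibly as written and the remedy is cheap. The randomised arm comparison is unaffected.

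**What to change.** Rewrite step d, with a matching sentence at the model comparison:

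- Replace the p ≤ 0.05 filter with one magnitude-based criterion, for example that covariates are dropped or combined only when VIF exceeds 5. The value 5 is conventional and is not taken from the documents. State which covariate is kept, or how a pair is combined, when the criterion is met.
- List the candidate covariates and write down the mediation/moderation model in advance. Keep covariates according to that model, not by p-value, whether the p-value comes from correlations between covariates or from the step-c associations with outcomes.
- State that the same retained set enters the comparison of the social-network and spatial-social models.

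The edit is a few sentences and needs no extra data. The real cost is drawing up a short candidate list and a model that do not yet exist in the plan. They must be limited to what 90 participants can support, because a lenient collinearity rule with a long list would invite overfitting.
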